With respect to SLE-CL, there is an ongoing clinical trial of TOFA in systemic SLE (NCT02535689) where adults with systemic SLE are dosed 5 mg BID. Further, there are several studies supporting the efficacy of TOFA in immune mediated alopecia as can occur with SLE-CL^{9,10}. Studies in children with *Juvenile Idiopathic Arthritis (JIA)*¹¹ suggest that TOFA is well tolerated. Overall, patients found the taste of the TOFA oral suspension to be acceptable (see abstract poster presentation 388 from 2016 ACR meeting¹² (see Appendix 1).

2. Study Design

[figure not shown]
A scheme of the study design and flow is shown in the **figure on the next page**.

This 76-week, 3-part Phase 1b/2 study is intended to evaluate the pharmacological properties (pharmacokinetics and pharmacodynamics), safety, tolerability and preliminary effectiveness of TOFA administrated to young adults (18-45 years) with moderately to severely active SLE-CL. Subjects will be studied at Cincinnati Children's Hospital Medical Center (CCHMC) and Metrohealth Medical Center.

- **Part A** (up to week 8) requires stable background medications;
- **Part B** (up to week 24) allows for tapering of *corticosteroids (CS) in the setting of significant clinical improvement of SLE-CL as defined by a decrease in Cutaneous Lupus Erythematosus Disease Area and Severity Index (CLASI) activity score by $\geq 50\%$ from baseline* , and
- **Part C** (until week 76) permits tapering of other background medications in subjects with clinical remission of SLE-CL (CLASI activity score=0). TOFA dosing is kept stable during Part C.

Cohort 1 (n=10, weight $> 40\text{kg}$ and age ≥ 18 years and ≤ 45 years) will undergo intense PK-sampling to determine exposures following TOFA dosed at 5 mg BID. TOFA dose escalation will not be considered for inadequate response of SLE-CL.

Cohort 2 (n=10, weight $> 40\text{kg}$ and age ≥ 18 years and ≤ 45 years) will be treated with the same dose as Cohort 1. No PK sampling will occur for Cohort 2.

All subjects discontinuing the study after TD1 will enter a 10-Week follow-up period (not shown in figure). TOFA – tofacitinib; study visits at trial day 1 (TD1), day 5 of week 1 **for Cohort 1 only**. Subjects will be discontinued for toxicity or lack of response to TOFA at week 8.

3. Trial Periods -Design

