4.3 Exploratory Objective(s) & Endpoint(s)

Exploratory objectives

Part A:

- To evaluate single cell expression patterns of skin biopsies of affected and non-affected skin with TOFA therapy
- To examine changes in interferon α/γ receptor, STAT phosphorylation patterns with TOFA therapy using immunohistochemistry
- To investigate mRNA expression patterns in peripheral blood upon treatment with TOFA with focus on interferon regulated genes

Parts B and C:

- To evaluate steroid sparing properties of TOFA for SLE-CL
- To evaluate TOFA effect of overall disease activity in SLE as measured by the SLEDAI and BILAG
- To evaluate effects of TOFA on quality of life as measured by the Skindex (appendix 4) and overall well-being

Exploratory endpoints at week 4, 8, 12, 24, 52, and 76

Part A: Pharmacodynamics (PD)

- PD parameters include assessment of inhibitory effect of TOFA on expression of IL-2 responsive target genes downstream of the JAK/STAT pathway, such as FOXP3, SOCS3, IL-2R α , interferon - γ and granzyme B.

Parts B and C:

- Decrease of absolute dose of systemic CS from baseline
- Decrease of body weight adjusted CS dose from baseline
 - CS dosing is measured in prednisone-equivalents
- Proportion of subjects who discontinue systemic CS
- Proportion of subjects with cutaneous relapse
- Change of BILAG score from baseline¹³
- Absolute value and percent change in plasma: Complement C3 and C4d, autoantibodies (anti-dsDNA)
- Change in number of inflamed joints from baseline¹⁴
- Change in SKINDEX score from baseline¹⁵
- Change of CLASI damage score¹⁶ from baseline
- Change in SLEDAI score at each time point
- Change in protein: creatinine ratio at each time point.
- Change in subject's overall well-being at each time point
- Change in subject's ESR
- Proportion of subjects with clinically important reduction in SLE activity at each time point, based on CRV changes compared to baseline
- Proportion of subjects with flare of SLE activity at each time point, as defined by the BILAG¹⁷

Data of subjects who enter Part B before week 8 and/or Part C before week 24 will be considered on a last-observation (LOC) carried forward basis for endpoints of Part A and B, respectively.

5. Study Participants

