6.5 Rescue clause, treatment failure & subject withdrawal

A subject will be considered a treatment failure and discontinued from the study if he/she experiences one or more of the following:

- Serious adverse event that is possibly related to TOFA;
- Important worsening of renal disease defined as a persistent increase in proteinuria as measured by the protein: creatinine (PC) ratio to values > 2.0 after achieving complete response of lupus nephritis, or doubling of proteinuria with values PC ratio > 3.0 after achieving a partial response of lupus nephritis;
- Need to increase current or initiation of new SLE background therapy due to non-renal SLE manifestations;
- Life-threatening SLE complications as judged by the investigator;
- Need for more than the protocol defined allowable CS rescue therapy as determined by the treating physician;
- No improvement of SLE-CL as measured by the CLASI by week 8;
- Two sequential absolute lymphocyte counts less than $< 0.5 \times 10^9$ or 500 cells/mm³;
- Two sequential hemoglobin values < 8.0 g/dL (80 g/L) or decreases greater than 2 g/dL on treatment;
- Female subjects that become pregnant during the study will discontinue study treatment. They will be continued to be followed in accordance as outlined in section **7.3.10**.

Subject Withdrawal

Subjects may withdraw from the study at any time at their own/their legal guardian's request, or they may be withdrawn at any time at the discretion of the physician investigators for safety, behavioral, or administrative reasons. If a subject does not return for a scheduled visit, every effort should be made to contact the subject. In any circumstance, every effort should be made to document subject outcome, if possible.

The investigator will inquire about the reason for withdrawal, request the subject to return all unused investigational product, request the subject to return for a final visit, if applicable, and follow-up with the subject regarding any unresolved AEs.

7 If the subject withdraws from the study, and also withdraws consent for disclosure of future information, no further evaluations should be performed, and no additional data should be collected. The sponsor may retain and continue to use any data collected before such withdrawal of consent. Planned Assessments & Evaluations

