7.1 Evaluations for ALL Subjects

PART A

Cohort 1: Subject will be monitored at Day 1 and Day 5 of week 1, and then once per week during weeks 2, 3, 4, 5, 6, 7, 8.
PK samples will be drawn on Day 5 of Trial Week 1: pre-morning dose and 0.5, 1, 2, 4 and 8 hours post-morning dose of Day 5.

Cohort 2: TD1, and then once per week during weeks 2, 3, 4, 5, 6, 7, and 8.

PART B[‡]

Subjects of Cohorts 1 and 2 will be monitored at study visits at weeks 10, 12, 16, 20 and 24. CS dosing can be changed during Part B.

PART C[§]

Subjects of Cohorts 1 and 2 will be monitored at study visits every 8 weeks until week 76. Background medications, CS and other background medications can be changed during Part C, while TOFA remains stable.

Follow-up Period

All subjects who discontinue TOFA treatment at any time post-baseline will have a follow up phone call 10 weeks after the last TOFA dose to monitor for the development of safety events.

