7.2 Evaluations Performed in Select Subjects

7.2.1 Photography & skin biopsy

A subset of up to 3-5 subjects from either Cohort 1 or Cohort 2 will be asked to participate in serial photography of lesions on the back, face or the extremities. Picture will be obtained three times during the study by a trained individual or medical photographer, starting from baseline (also see Schedule of Events).

Subjects agreeing to participate in photography will also be asked to consent to two skin biopsies. At each of the two biopsy sessions 2 skin samples will be obtained (approximately 3 mm in diameter) by means of punch biopsy. The first two skin biopsy samples will be taken from an active SLE-CL lesion located over the back or the extremities during week 1. The second two skin biopsy samples will be taken from the initial lesion, in close geographical proximity to the site of the initial biopsy, between weeks 8 and 15.

Prior to taking the skin biopsy the area will be numbed with topical or injectable lidocaine.

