Medical history, medication		X																					
Tuberculosis assessment		X																					
Serum virology (HBsAg, HCV, HIV, VZV)		X																					
Serum pregnancy test*2		X																					
Urine pregnancy test*2			X		X						X		X		X	X	X	X	X	X	X	X	
Vital sign, weight, height*3		X	X	X	X	X	X	X	X	X	X	X	X	X	X	X	X	X	X	X	X	X	
Investigational Product Dispensing (or as needed)			X				X				X		X	X	X	X	X	X	X	X	X	X	X
Patient Dosing Diary review				X	X	X	X	X	X	X	X	X	X	X	X	X	X	X	X	X	X	X	
Complete physical examination		X	X			X					X		X	X	X	X	X	X	X	X	X	X	X
Laboratory Assessment																							
Hematology		X	X	X	X	X	X	X	X	X	X	X	X	X	X	X	X	X	X	X	X	X	
Clinical chemistry		X	X	X	X	X	X	X	X	X	X	X	X	X	X	X	X	X	X	X	X	X	
Urinalysis incl. sediment		X	X			X					X		X	X	X	X	X	X	X	X	X	X	
Urine protein: creatinine ratio		X	X			X					X		X	X	X	X	X	X	X	X	X	X	
Complement C3, C4,			X			X					X		X	X	X	X	X	X	X	X	X	X	
ANA*4 and anti-ds DNA Abs			X			X					X		X	X	X	X	X	X	X	X	X	X	
ESR			X			X					X												X
Efficacy																							
CLASI		X	X	X	X	X	X	X	X	X	X	X	X	X	X	X	X	X	X	X	X	X	
Photography (selected)			X							X													
SLICC/ACR damage index			X								X												X
SLEDAI-2K, MD Global Assessments, BILAG			X			X					X		X	X	X	X	X	X	X	X	X	X	
Patient's Global Assessment, Skindex			X			X					X		X	X	X	X	X	X	X	X	X	X	
Pharmacokinetic																							
Plasma TOFA-Part A (Cohort 1) *5			X*6																				
Pharmacodynamic																							
**Gene expression profiling of IL2 mediated genes in whole blood					X						X						X						
**Phosphospecific flow cytometry of blood T-cells & other relevant cells					X						X						X						
**SC-RNA SEQ in skin biopsies (selected)				X														X					
**Skin biopsy (selected) *7			X														X *7						
Safety																							
Adverse events/SAE		X	X	X	X	X	X	X	X	X	X	X	X	X	X	X	X	X	X	X	X	X	
Concomitant medications		X	X	X	X	X	X	X	X	X	X	X	X	X	X	X	X	X	X	X	X	X	
TT, diphtheria, varicella, influenza titer; EBV and CMV PCR		X															X						

¹*Part A - Day 5 after TD1

²Females only

³Height only at screening

⁴ANA only at baseline on TD1

⁵ A total of 24.5 mL of blood will be taken at these visits for pharmacodynamics tests

⁶PK samples will be drawn on Day 5 of Trial Week 1. re - morning dose for Day 5 and at 0.5, 1, 2, 4 and 8 hours post morning dose.

⁷ Two 3mm punch biopsies will be collected. 1st punch collected during week one. 2nd punch collected between weeks 8-15.

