All data will be entered into the Medidata Rave database on PCs in the Division of Rheumatology, CCHMC, stored and accessed in accordance with the HIPPA Standards [www.hhs.gov], HCFA's Internet Security Policy and other state and local requirements. The Medidata Rave database is maintained on servers by Medidata and back up is performed as outlined by medidata information security and privacy white paper. The Division of Biomedical Informatics at CCHMC distributes numerous computer packages for research purposes, including SAS [SAS Inc., Cary, North Carolina) and Microsoft software [see <http://info.chmcc.org>). Data monitoring of data collected at the CCHMC will be performed by the Division of Rheumatology research staff with assistance from the CCHMC *Office for Clinical and Translational Research* (OCTR).

MONITORING OF SITES

The PI will monitor the database of both CCHMC and Metrohealth Medical Center with assistance from CCHMC OCTR.

REPORTING OF ADVERSE EVENTS

Reporting of Adverse events will occur as part of the safety assessment of the study drug. We will use the National Cancer Institute (NCI) Common Toxicity Criteria, Version II for reporting.

All severe adverse events communicated to CC within one working day will be reported to the IRB within 2 working days. Based on the requirements for IND amendments outlined in the CFR §312.32, [name] will be responsible for IND safety reporting including reporting of life-threatening and serious adverse events, unexpected adverse drug experience and the writing of the annual IND safety report.

CRITERIA FOR STUDY DISCONTINUATION

A subject will be considered a treatment failure and discontinued from the study if he/she experiences one or more of the following:

- Serious adverse event that is possibly related to TOFA;
- Important worsening of renal disease defined as a persistent increase in proteinuria as measured by the protein: creatinine (PC) ratio to values > 2.0 after achieving complete response, or doubling of proteinuria with values PC ratio >3.0 after achieving a partial response;
- Need to increase current or initiation of new SLE background therapy due to non-renal SLE;

- Life-threatening SLE complications as judged by the investigator;
- Need for more than the allowable CS rescue therapy as determined by the treating physician.
- No response of SLE-CL by Week 8

INTERIM ANALYSIS & SAFETY REVIEWS

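### The weeks 8 to 15 window for the second skin biopsy can place it after the week-8 exit for lack of response, so the exploratory tissue pairs can lose non-responders and can follow a steroid change

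*Combined protocol and SAP*

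**What the plan says.** **Biopsy timing.** Section 7.2.1 asks "A subset of up to 3-5 subjects from either Cohort 1 or Cohort 2" to take part. The first samples are taken in week 1 and the second from the same lesion, "in close geographical proximity to the site of the initial biopsy, between weeks 8 and 15". Footnote 7 to the Schedule of Assessments (Section 10) agrees: "2nd punch collected between weeks 8-15".

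**Purpose.** Section 4.3 lists the tissue objectives under Part A. One is "To examine changes in interferon α/γ receptor, STAT phosphorylation patterns with TOFA therapy using immunohistochemistry"; another concerns single-cell expression in biopsied skin. Section 8.3 says only that these patterns will be explored.

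**Exit at week 8.** Section 2 states: "Subjects will be discontinued for toxicity or lack of response to TOFA at week 8". Section 6.5 lists among the treatment-failure criteria "No improvement of SLE-CL as measured by the CLASI by week 8". Appendix 3, Section H, has "No response of SLE-CL by Week 8". Section 7.1 describes follow-up after stopping tofacitinib as a phone call 10 weeks after the last dose.

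**Steroids.** Section 3 holds all background medication, steroids included, unchanged in Part A. Section 7.1 says of the next part: "CS dosing can be changed during Part B". Section 6.2, however, allows a decrease from week 5, and Sections 3 and 6 let subjects in skin remission enter Part B from week 4.

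**The concern.** A before-and-after tissue comparison is useful only if having the second sample does not depend on the outcome that the tissue is meant to explain. Here it can. From the day after the week-8 visit, a subject is available for an on-drug second sample only if the skin improved or responded well enough to stay in the study. A sample taken later from a subject who has left would be off drug; the only half-lives in the documents, in Appendix 1 for children with arthritis, are 1.77 to 2.62 hours.

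The same late dates are those at which steroids may be changed. Where steroids are given mainly for the skin disease, Sections 3 and 6.2 tie a decrease to an improvement of at least 50% in CLASI activity, so those changes would be concentrated in strong responders. With so few subjects, losing one non-responder could remove the contrast between responders and non-responders altogether.

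**Working it through.** The plan states no sample size, error rate or effect size for the tissue work, so there is no figure to reproduce. The check covers the timeline and the possible loss of pairs.

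**Timeline**

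| Event | Time | Source |
|---|---|---|
| Second biopsy | weeks 8 to 15 | 7.2.1; Section 10, footnote 7 |
| Exit for lack of improvement or response | week 8 | 2; 6.5; Appendix 3, Section H |
| Scheduled visits inside the biopsy window | weeks 8, 10, 12 | 7.1 |
| Biopsy required at exit | none stated | 6.5, 7.1, 7.2.1 |
| Steroids held unchanged | to week 8 | 3 (Part A) |
| Steroid decrease allowed | from week 5 | 6.2 |
| Earliest entry to Part B | week 4, in remission | 3; 6 |
| Earliest entry to Part C, where all therapies except tofacitinib may change | week 8, in remission and off steroids | 3; 4.1, note |

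Of the three scheduled visits in the window, only week 8 comes before the exit rule takes effect.

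**Chance of losing pairs**

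Inputs: n = 3 to 5 biopsied subjects (7.2.1). The share f leaving at week 8 for lack of improvement or response is not in the documents; 20% to 30% is assumed.

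*Case 1: every second sample is taken after week 8.* Each exiting subject loses the pair.
- P(at least one pair lost) = 1 − (1 − f)^n
- f = 20%: 1 − 0.8³ = 49%; 1 − 0.8⁵ = 67%
- f = 30%: 1 − 0.7³ = 66%; 1 − 0.7⁵ = 83%
- Expected pairs lost, n × f: 0.6 to 1.0 at 20%; 0.9 to 1.5 at 30%

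*Case 2: second samples are spread evenly over the visits at weeks 8, 10 and 12 (assumption).* One third of exiting subjects are sampled in time, so f is replaced by 2f/3.
- f = 20%: 2f/3 = 13.3%; 1 − 0.867³ = 35%; 1 − 0.867⁵ = 51%
- f = 30%: 2f/3 = 20%; 1 − 0.8³ = 49%; 1 − 0.8⁵ = 67%
- Expected pairs lost: 0.4 to 0.67 at 20%; 0.6 to 1.0 at 30%

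*Sensitivity to f, case 1.* At f = 10% the chance is 27% to 41% (1 − 0.9³; 1 − 0.9⁵). At f = 50% it is 88% to 97% (1 − 0.5³; 1 − 0.5⁵).

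*Case 3: every second sample is taken at the week-8 visit, before exit.* Loss through the week-8 rule is zero. Subjects who stop earlier for other reasons are still lost.

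**Steroids**

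Section 3 expects up to 80% of subjects to take steroids, which is at most 0.8 × 3 = 2.4 to 0.8 × 5 = 4.0 of the biopsied subjects. That is the share who could have a change, not the share who will. The number whose dose changes before the second sample cannot be derived from the documents.

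**The case against.** - **Loss is permitted, not built in.** Week 8 lies inside the window, so a subject about to be discontinued may be sampled at that visit. This stands, and it is why case 2 is given beside case 1.
- **The exit rule may not remove all non-responders.** Under the wording in Section 6.5 only subjects with no improvement leave. Someone with a small improvement, below the 20% that Section 4.2 requires for a partial response, is a non-responder who stays. Section 2 and Appendix 3, Section H, speak of response, which points to a wider exit. A reader might infer that the tissue results would come from improvers only; the documents do not support that.
- **A Part A label does not fix the sample at week 8.** Section 4.3 lists exploratory endpoints, including the Part A pharmacodynamic ones, at weeks 4 through 76. This stands; the point rests on the exit rule and the steroid rules, not on the label.
- **The steroid argument has limits.** Decreases are conditional or at the investigator's discretion, and subjects not taking steroids are unaffected. The direction of any distortion is not determined: lowering an anti-inflammatory drug could mask a fall in inflammatory signalling rather than mimic one.
- **The work is exploratory.** It involves a handful of volunteers at one site, and Section 8.3 defines no test and no mean change. A reader might want to state a percentage by which the drug effect is overstated. The plan defines no quantity to which such a percentage could apply.

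**Conclusion.** The point holds as a weakness that the plan permits. The window allows the second sample to fall after the week-8 exit, nothing secures a sample from those who leave, and later samples can follow a steroid change. With the assumed 20% to 30% exit share, the chance of losing at least one of 3 to 5 pairs is 49% to 83% if all second samples come after week 8, and about 35% to 67% if they are spread over weeks 8, 10 and 12. Both ranges rest on that assumption, and on exits being independent between subjects.

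It would be tempting to add that a week-8 sample settles the steroid question. It does not. Section 3 holds steroids unchanged in Part A, Section 6.2 allows a decrease from week 5, and early entry to Part B is possible from week 4. A week-8 sample can therefore already follow a dose change, most readily in subjects in remission. The primary endpoints and the secondary CLASI response endpoint are not affected.

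**What to change.** 1. In Section 7.2.1 and footnote 7, set the second research sample at the existing week-8 visit. At minimum, require it at that visit for any biopsied subject about to be discontinued, whatever the CLASI result. Subjects who enter Part B early keep the same visit schedule to week 8 (Section 3), so the visit exists for them too.
2. In Section 8.3, state that the steroid dose at each biopsy will be used, that pairs will be shown by response and by steroid change, and that missing second samples will be listed with the reason. Concomitant medications are already collected.
3. Reconcile the steroid-timing passages (Section 3, Part A; Section 6.2; early Part B entry in Sections 3 and 6), and the week-8 exit wording in Section 6.5 against Section 2 and Appendix 3, Section H. A week-8 sample is free of steroid change only if steroids are in fact unchanged to that visit.

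The cost is a short amendment and less scheduling flexibility at the one site that takes biopsies. No extra biopsy, visit or subject is needed.

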7.2.2 Pharmacokinetic parameters

Plasma TOFA levels

Cohort 1 will undergo intensive sampling in week 1.

7.2.3 Exploratory Pharmacodynamic Biomarkers

A subset of subjects will be asked to participate in translational research studies, performed 2 or 3 times during the study.

- Blood samples for RNA and miRNA level gene expression with focus on interferon regulated pathways
- Interferon γ and interferon α levels
- T cell activation of flow – C1 or POLARIS
- Urine biomarkers
- Single-cell RNA sequencing of skin cells
- Immunohistochemistry of skin cells for phosphorylated STATs and interferons

7.3 Safety & Adverse Event Reporting

Safety reporting will be completed in accordance with IRB guidelines and FDA requirements (21 CFR Part 312) for studies performed under an IND.

7.3.1. Adverse Events

All observed or volunteered *Adverse Events* (AE) will be reported as described in the following sections.

For all AEs, the site's investigator must pursue and obtain information adequate both to determine the outcome of the AE and to assess whether it meets the criteria for classification as a *Serious Adverse Event* (SAE) requiring immediate notification to the IRB and Pfizer or its designated representative. For all AEs, sufficient information should be obtained by the investigators to determine the causality of the AE. The investigators will assess causality. Follow-up by the investigator may be required until the event or its sequelae resolve or stabilize at a level acceptable to the IRB, the investigator, and Pfizer concurs with that assessment.

As part of ongoing safety reviews conducted by the Principal Investigator, any non-serious adverse event that is determined by the Principal Investigator (PI) to be serious will be reported by the PI as a SAE.

